7.4.4 Analysis of Exploratory Endpoints

Central FLT3 mutation status at screening, including subgroups of FLT3-ITD mutation and D835/I836 TKD mutations, will be summarized by the number and percentage of subjects in each category by treatment group. An exploratory analysis of FLT3 mutation type and selected clinical efficacy endpoints will be conducted (see Section 7.8).

Additional biomarker exploratory analysis on AXL status, FLT3 related biomarkers and other genes mutations will be performed and the details will be included in a separate Biomarker Statistical Analysis Plan (Biomarker SAP).

Incidence of resource utilization including hospitalization, blood transfusion, antibiotic intravenous infusions, medication for AEs and opioid medication during the entire study period will be summarized by treatment group. The difference between treatment groups will be tested using CMH test while controlling for response to first-line AML therapy and preselected salvage chemotherapy. Duration of hospital stays, medication for AEs and opioid medication will be summarized by treatment group using descriptive statistics (mean, standard deviation, minimum, maximum and median). The difference between treatment groups will be tested with ANOVA while controlling for response to first-line AML therapy and preselected salvage chemotherapy.

FACIT-Dys-SF domain scores will be summarized by treatment group at each visit using descriptive statistics (mean, standard deviation, minimum, maximum and median). Additionally, a within-subject change will be calculated as the post-baseline score minus the baseline score and summarized in the same way. ANCOVA model will be used to analyze the change in the FACIT-Dys-SF domain scores from baseline to post-baseline visits including treatment as a fixed factor, baseline score, response to first-line AML therapy and preselected salvage chemotherapy as covariates.

FACT-Leu global score and domain scores will be summarized by treatment group at each visit using descriptive statistics (mean, standard deviation, minimum, maximum and median). Additionally, a within-subject change will be calculated as the post-baseline score minus the baseline score and summarized in the same way. ANCOVA model will be used to evaluate change from baseline to post-baseline visits for the global and domain scores, of the FACT-Leu including treatment as a fixed factor, baseline score, response to first-line AML therapy and preselected salvage chemotherapy as covariates. The same analytic approach will be used for the dizziness and mouth sore items.

EQ-5D-5L VAS will be summarized by treatment group at each visit using descriptive statistics (mean, standard deviation, minimum, maximum and median). Additionally, a

within-subject change will be calculated as the post-baseline score minus the baseline score and summarized in the same way. ANCOVA model will be used to evaluate change from baseline to post-baseline visits for the EQ-5D-5L VAS including treatment as a fixed factor, baseline score, response to first-line AML therapy and preselected salvage chemotherapy as covariates. Shift table showing shift in each dimension score from baseline to each post-baseline visit will be provided for the 5 dimensions (mobility, self-care, usual activities, pain/discomfort and anxiety/depression).

Additional exploratory analysis of patient reported outcomes (BFI, FACIT-Dys, FACT-Leu, dizziness, mouth sore items) and heath outcome (EQ-5D-5L) will be performed and the details will be included in a separate Patient Reported Outcome Statistical Analysis Plan (PRO SAP).

Additional exploratory analysis of resource utilization with regard to health economic model will be performed and the details will be included in a separate Health Economic Statistical Analysis Plan.

7.4.5 Analysis of Other Variables

Best Response will be summarized by treatment group. The number and percentage of subjects in each category will be presented. The best response rate by prior FLT3 inhibitor use will also be summarized.

At the first interim analysis, Time to first and best CR/CRh (TTCRCRh) will be summarized using descriptive statistics (mean, standard deviation, minimum, maximum and median) for subjects who achieved either CR or CRh in the same analysis set of CR/CRh rate.

TTCRc, TTCR, TTR will be summarized by treatment group using descriptive statistics (mean, standard deviation, minimum, maximum and median) for subjects who achieved remission in the ITT.

7.4.6 Analysis of CR/CRh rate, Duration of CR/CRh and Time to first and best CR/CRh at Final Analysis

The CR/CRh rate, Duration of CR/CRh and Time to first and best CR/CRh will be summarized descriptively on both arms at the final analysis.

The CR/CRh rate will be evaluated in the same manner as CR rate using CMH test to control for response to first-line AML therapy and preselected salvage chemotherapy on ITT. The number and percentage of subjects with CR/CRh will be summarized for each treatment group along with exact 95% confidence interval based on binomial distribution. The treatment difference along with 95% confidence interval will be calculated.

The sensitivity analysis for CR/CRh rate will be performed to assess the robustness of the CR/CRh rate as follows:

- The same analysis as primary analysis but on FAS
- The same analysis as primary analysis but on PPS

Sponsor: Astellas Pharma Global Development, Inc.

ISN/Protocol 2215-CL-0301

- The same analysis as primary analysis but only including ITT subjects who took at least one dose of study drug
- The same analysis as primary analysis but only including ITT subjects who had at least one post baseline bone marrow assessment
- Apply the same analysis method used for primary analysis to evaluate CR/CRh rate prior to HSCT (as defined in Section 6.1.2)
- The same analysis as primary analysis for CR/CRh rate will be performed by dose adjustment in ASP2215 arm.

Duration of CR/CRh (DCRCRh) and Time to first and best CR/CRh (TTCRCRh) will be summarized in the same manner as Duration of CR (as specified in Section 7.4.3.2) and Time to CR (as specified in Section 7.4.5), respectively, for subjects who achieved either CR or CRh on ITT. Median follow-up of DCRCRh estimated from reverse Kaplan-Meier curve will be provided.

As a sensitivity analysis, Duration of CR/CRh will also be analyzed with deaths without report of relapse considered as events (as defined in Section 6.1.3.2). In addition, Duration of CR/CRh will also be analyzed by subjects with or without transplantation during the study period.

7.5 Analysis of Safety

All analysis of safety will be presented by treatment group for SAF, unless specified otherwise.

7.5.1 Adverse Events

All adverse event (AE) recorded on treatment including within 30 days from the last study treatment will be summarized.

Summaries and listings of SAEs and Serious TEAEs include SAEs upgraded by the sponsor based on review of the Sponsor's list of Always Serious terms if any upgrade was done.

The coding dictionary for this study will be MedDRA. It will be used to summarize AEs by SOC and PT. AEs will be graded using National Cancer Institute's Common Terminology Criteria for AEs (NCI-CTCAE).

An overview table to report the number and percentage of subjects and an overview table to report number of events and events adjusted by patient year from drug exposure will include the following details:

- TEAEs,
- Drug-related TEAEs,
- Serious TEAEs,
- Drug-related serious TEAEs,
- TEAEs leading to death
- Drug-related TEAEs leading to death
- TEAEs leading to withdrawal of treatment,

- Drug-related TEAEs leading to withdrawal of treatment,
- Grade 3 or higher TEAEs,
- Drug-related Grade 3 or higher TEAEs,
- Any death

The number and percentage of subjects with TEAEs and the number of events and events adjusted by patient year from drug exposure, as classified by SOC and PT will be summarized for each treatment group. Summaries will be provided for:

- TEAEs
- Drug-related TEAEs,
- Serious TEAEs,
- Drug-related serious TEAEs,
- TEAEs leading to death
- Drug-related TEAEs leading to death
- TEAEs leading to withdrawal of treatment,
- Drug-related TEAEs leading to withdrawal of treatment,
- Grade 3 or higher TEAEs,
- Drug-related Grade 3 or higher TEAEs

The number and percentage of subjects with TEAEs, as classified by SOC and PT will also be summarized for each treatment group for the following:

• TEAEs excluding serious adverse events that equal to or exceed a threshold of 5% in any treatment group,

The number and percentage of subjects with TEAEs, as classified by PT only, will also be summarized for each treatment group for the following:

- TEAEs
- Drug-related TEAEs,

The number and percentage of subjects with TEAE of special safety interest (AESI), as classified by AESI category and PT will be summarized for each treatment group for the following:

- TEAEs with special safety interest,
- Grade 3 or higher TEAEs with special safety interest,
- Drug-related Grade 3 or higher TEAEs with special safety interest

AE summary tables will include subject counts as opposed to AE counts. If a subject experiences more than one episode of a particular AE, that subject will be counted only once for that event. If a subject has more than one AE that code to the same preferred term, the subject will be counted only once for that preferred term. Similarly, if a subject has more than one AE within a body system, the subject will be counted only once in that body system.

All AEs, deaths, SAEs and withdrawals due to adverse events will be displayed in listings.

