- k. For MEC and FLAG-IDA, bone marrow samples are required during screening and cycle 2 day 1. Also, an additional bone marrow sample is required at cycle 1 day 15 or later, per institutional guidelines, to assess the need for a second cycle. For LoDAC or azacitidine, bone marrow samples are required during screening, and at cycle 2 day 1 and at cycle 3 day 1. For subjects who do not achieve a CRc (CR, CRp or CRi), the bone marrow assessments will be repeated at day 1 of every 2 subsequent cycles. For subjects who achieve a CRc (CR, CRp or CRi), bone marrow sampling will be repeated at 1 month after the date of remission and every 3 subsequent cycles, or if there is suspicion of relapse in the whole blood. Bone marrow samples are also required at the end of treatment visit and as clinically indicated. If bone marrow aspirate is unobtainable (e.g., dry tap), an additional EDTA tube of peripheral blood should be collected instead. Bone marrow aspirate is required, and bone marrow biopsy is preferred. In case of inadequate aspirate, bone marrow biopsy is required.
- 1. Whole blood and buccal swab collected at day 1 for optional pharmacogenomic study.
- m. LoDAC or azacitidine dosing may continue past cycle 2.
- n. Additional clinic visits are allowed per institutional guideline for subjects receiving MEC (days 1 through 5) or FLAG-IDA (days 1 through 6). MEC and FLAG-IDA are administered for up to 2 cycles depending on response and safety assessments as described in Section 5.1 of the protocol.
- o. Chest X-ray (or CT of chest) does not need to be repeated if performed within 2 weeks prior to start of screening.
- p. For the purposes of drug preparation and dispensing activities, IRT transaction may be done prior to the visit and do not need to fall within the protocol visit window.

Footnotes continued on next page.

- q. Includes Brief Fatigue Inventory, Functional Assessment of Chronic Illness Therapy–Dyspnea-Short Forms, Functional Assessment of Cancer Therapy-Leukemia and dizziness and mouth sores items. The BFI will be administered at cycle 1 day 1 predose, cycle 1 day 8 (± 1 day), day 15 (± 1 day), cycle 2 day 1 (± 2 days), day 15 (± 1 day) and all subsequent cycles day 1 (± 2 days). Functional Assessment of Chronic Illness Therapy–Dyspnea-Short Forms, Functional Assessment of Cancer Therapy-Leukemia and dizziness and mouth sores items will be administered at cycle 1 day 1 predose, cycle 2 day 1 (± 2 days) and all subsequent cycles day 1 (± 2 days).

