6.2 Safety Variables

Safety will be assessed by evaluation of the following variables:

- Treatment-emergent adverse events (TEAEs; frequency, severity, CTCAE grade, seriousness, and relationship to study drug)
 - o TEAE is defined as an adverse event observed after starting administration of the study treatment (ASP2215 or salvage chemotherapy). If the adverse event occurs on Day 1 and the onset check box is marked "Onset after first dose of study drug" or the onset check box is left blank, then the adverse event will be considered treatment emergent. If the adverse event occurs on Day 1 and the onset check box is marked "Onset before first dose of study drug", then the adverse event will not be considered treatment emergent. If a subject experiences an event both during the preinvestigational period and during the investigational period, the event will be considered as TEAE only if it has worsened in severity (i.e. it is reported with a new start date). All adverse events collected that begin within 30 days after taking the last dose of study drug will also be counted as TEAE, except for subjects that undergo HSCT without leaving the study and plan to resume ASP2215 treatment after HSCT. For these subjects, TEAE is defined as adverse events observed after starting administration of the study treatment until the last dose before pre-HSCT visit plus 30 days, and adverse events that begin after resumption of ASP2215 and within 30 days after the last dose of ASP2215 will also be counted as TEAE. Any AEs with onset dates completely missing will be considered TEAEs in summaries. AEs with partially missing onset dates will be assumed TEAEs unless the available portion of the date indicates that the onset was strictly before start of study medication or 30 days after the last study treatment. Missing or partial AE onset date will be imputed per Section 7.11.1.
 - A drug-related TEAE is defined as any TEAE with at least possible relationship (possibly or probably related) to study treatment as assessed by the investigator or with missing assessment of the causal relationship
- Serious adverse events (SAEs) include adverse events that are flagged as serious by the investigator on eCRF, or upgraded by the Sponsor based on review of the Sponsor's list of Always Serious term.
- Adverse events of special safety interest (AESI) are defined in the Safety Review Plan for ASP2215 (as specific in Section 10.3, Appendix 3).

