6.4 Other Variables

Duration of exposure

Duration of exposure to each component of a study drug will be calculated in days, using the following formula:

Last date of exposure – First dose date + 1 – (on-study HSCT period for subjects undergo on-study HSCT)

For ASP2215, last date of exposure = last dose date of ASP2215

For chemotherapy, last date of exposure = (initial dose date of the last cycle +28-1) or death date if death occur within last cycle

When the start or stop date is missing, then the exposure will be treated as missing.

Duration of exposure for a chemotherapy regimen, i.e. MEC and FLG-IDA, will be the maximum (duration of exposure of all treatment components).

When the last date of exposure is beyond cutoff date, the cutoff date will be used as the last date of exposure.

Number of dosing days

Number of days with non-zero dosing.

Number of cycles

Number of cycles for each component of study drug refers to total number of cycles with non-zero dosing in the cycle.

Number of cycles for a chemotherapy regimen refers to total number of cycles with non-zero dosing of any treatment component in the cycle.

• Cumulative dose (dose unit)

Cumulative dose will be calculated using the following formula for each type of study drug:

- ASP2215: Sum of [(stop date start date + 1) * dose captured on dosing CRF] across all records
- LoDAC: Sum of (number of dose taken * 20mg) across all records and all cycles.
 If number of dose take is "unknown", it will be treated as missing.
- Azacitidine: Sum of (number of dose taken * actual delivered dose captured on dosing CRF) across all records and all cycles. If number of dose taken is "unknown", it will be treated as missing.

 Each component of MEC and FLAG-IDA: Sum of (actual delivered dose captured on dosing CRF) across the days when study drug was administered. If answer to "entire infusion administered" is No, actual delivered dose will be treated as missing.

• Average daily dose (dose unit/days)

Cumulative dose (dose unit)

Number of dosing days (days)

Dose intensity

Dose intensity will be calculated in mg/day for ASP2215 as:

Cumulative dose (mg)

Duration of exposure (days)

Dose intensity will be calculated in dose unit/cycle for chemotherapy as:

Cumulative dose (dose unit)

----- x 28 (days/cycle)

Duration of exposure (days)

• Relative dose intensity

Relative dose intensity for ASP2215 will be calculated as:

Dose intensity (mg/day)

-----x 100%

120 (mg/day)

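### Patient-year adverse event rates count events to 30 days after the last dose but appear to divide by exposure time that ends earlier, by a different rule in each arm

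*SAP*

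**What the plan says.** **Numerator.** SAP Section 7.5.1 states: "All adverse event (AE) recorded on treatment including within 30 days from the last study treatment will be summarized". Section 6.2 agrees: "All adverse events collected that begin within 30 days after taking the last dose of study drug will also be counted as TEAE". For subjects who have an on-study HSCT and plan to resume ASP2215, Section 6.2 counts events to 30 days after the last pre-HSCT dose, and again from resumption to 30 days after the final dose.

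**Denominator.** Section 7.5.1 asks for the "number of events and events adjusted by patient year from drug exposure", in an overview table and in ten summaries by system organ class and preferred term. It gives no formula. The only exposure duration in the SAP is in Section 6.4: "Last date of exposure – First dose date + 1 – (on-study HSCT period for subjects undergo on-study HSCT"). Its end date differs by arm:
- ASP2215: "For ASP2215, last date of exposure = last dose date of ASP2215".
- Chemotherapy: "For chemotherapy, last date of exposure = (initial dose date of the last cycle +28-1"), or the date of death if that falls within the last cycle.

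In both arms, exposure that would run past the data cutoff is cut there. No section adds the 30 post-dose days to the patient-years or defines a separate time at risk.

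**The concern.** A rate per patient-year is meant to make arms with unequal follow-up comparable. That requires the events and the time to come from the same window. Here events come from a longer window than the time, so the rate is too high. The excess is relatively largest where exposure is short.

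The two arms also end exposure by different rules. The ASP2215 denominator includes none of the 30 post-dose days. The chemotherapy denominator runs on to day 28 of the last cycle and so already includes most of them. Unequal exposure is built into the design: MEC and FLAG-IDA are limited to two cycles (Section 2, Table 2 footnote n), while ASP2215, LoDAC and azacitidine continue until a discontinuation criterion is met (Section 3.2.1). Two arms with the same true event rate could therefore show different reported rates. Safety is the only analysis planned for the end-of-study report (Sections 1 and 3.2.1), so these tables will be read there.

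**Working it through.** The SAP states no adverse event rate or patient-year total, so there is no figure of its own to reproduce.

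**Inputs**
- Event window: last dose + 30 days (Sections 6.2 and 7.5.1).
- End of exposure: last dose (ASP2215) or day 28 of the last cycle (chemotherapy) (Section 6.4).
- Last dosing day in a cycle: 5 for MEC and 6 for FLAG-IDA, from "subjects receiving MEC (days 1 through 5) or FLAG-IDA (days 1 through 6" in Section 2. It is 7 for azacitidine and 10 for LoDAC, from the dosing days per cycle in Section 6.4, assuming consecutive dosing from day 1. If FLAG-IDA ends on day 5, as the dosing days in Section 6.4 would give, it behaves like MEC.
- Exposure in days: not in the SAP. The ASP2215 values of 60, 180 and 365 days and the one or two chemotherapy cycles are illustrative.

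**Days in the numerator but not the denominator**
- ASP2215: 30.
- Chemotherapy: (last dosing day + 30) − 28. MEC 35 − 28 = 7; FLAG-IDA 36 − 28 = 8; azacitidine 37 − 28 = 9; LoDAC 40 − 28 = 12. The chemotherapy denominator thus already covers 18 to 23 of the 30 days.

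**Inflation factor** = (exposure days + uncovered days) / exposure days, with a constant event rate and a fully observed 30-day window.

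| Treatment | Exposure (days) | Factor |
|---|---|---|
| ASP2215 | 60 | 90/60 = 1.50 |
| ASP2215 | 180 | 210/180 = 1.17 |
| ASP2215 | 365 | 395/365 = 1.08 |
| MEC | 28; 56 | 35/28 = 1.25; 63/56 = 1.13 |
| FLAG-IDA | 28; 56 | 36/28 = 1.29; 64/56 = 1.14 |
| Azacitidine | 28; 56 | 37/28 = 1.32; 65/56 = 1.16 |
| LoDAC | 28; 56 | 40/28 = 1.43; 68/56 = 1.21 |

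**Reported ASP2215/chemotherapy ratio when the true ratio is 1** (ASP2215 factor divided by chemotherapy factor; each range runs from LoDAC to MEC)

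| ASP2215 exposure | One chemotherapy cycle | Two chemotherapy cycles |
|---|---|---|
| 60 days | 1.05 to 1.20 | 1.24 to 1.33 |
| 180 days | 0.82 to 0.93 | 0.96 to 1.04 |
| 365 days | 0.76 to 0.87 | 0.89 to 0.96 |

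The factors are equal when ASP2215 exposure = 30 × chemotherapy exposure / uncovered chemotherapy days. Against MEC this is 30 × 28/7 = 120 days for one cycle and 30 × 56/7 = 240 days for two. Below that point ASP2215 looks worse than it is relative to MEC; above it, better.

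**Sensitivity to the post-dose event rate.** Take 84 days of ASP2215 against two cycles of MEC. The factors are (84 + 30)/84 = 1.36 and 1.13. If events after the last dose occur at half the on-treatment rate, they fall to (84 + 15)/84 = 1.18 and (56 + 3.5)/56 = 1.06. At a quarter, they are 1.09 and 1.03.

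**The case against.** The case on the other side has six parts.

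- **The denominator is inferred.** Section 7.5.1 does not cite Section 6.4, and Section 7.1 leaves table formats to specifications that are not part of the SAP. This stands as a caveat. However, the wording refers to drug exposure and the SAP defines no other exposure time.
- **The measure is partly conventional.** The revision history says the patient-year summaries were added for consistency with the ISS, and the SAP calls them exposure-adjusted, not time at risk. That explains why they are there; it does not align the windows. It is a good reason to keep the exposure-only rates available.
- **The size is conditional.** The window is shortened by death (Section 4 assumes median survival of only 5 to 7.7 months), by the data cutoff and by the start of conditioning. An ASP2215 subject still on drug at the cutoff has no mismatch. This stands.
- **No single factor fits every row.** Events leading to withdrawal of treatment should arise mostly on treatment and would move little. This stands.
- **The HSCT element is limited.** Section 2, Table 3 footnote e stops general event collection at conditioning and continues only listed categories to 30 days. Section 6.4 does not say when the on-study HSCT period starts, so the number of counted days it removes is unknown. This stands.
- **The tables are descriptive.** No test, boundary or decision rule uses them, and subject counts and percentages are shown too. This stands, and it limits the importance of the point.

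**Conclusion.** The point holds in a limited form. As written, numerator and denominator cover different time, and the gap differs by arm: up to 30 days for ASP2215, and about 7 to 12 for chemotherapy. Under a constant event rate and a fully observed window, the inflation is about 1.5-fold at short ASP2215 exposure and about 1.1-fold at one year, against 1.13 to 1.43 for one or two chemotherapy cycles. It is smaller if events become rarer after the last dose or the window is cut short.

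Three stronger readings are tempting but not supported:
- A reader might infer that the rates favour one arm. The distortion changes sign with exposure, which the SAP does not give.
- A reader might take the one-cycle comparison at 365 days (0.76 to 0.87) as the expected size. Two cycles give 0.89 to 0.96, and LoDAC and azacitidine may run longer.
- A reader might conclude that the safety comparison as a whole is compromised. Only the patient-year tables are affected. Subject percentages and all efficacy analyses are untouched.

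This should be corrected, because the rates do not do the job they were added for, but it does not threaten the trial's main conclusions.

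**What to change.** In Section 7.5.1, define patient-years as time at risk for treatment-emergent events, by the same rule in both arms:
- Count from first dose to the earliest of last dose + 30 days, death or data cutoff.
- For subjects who resume ASP2215 after HSCT, add together the pre-HSCT period with its 30 days and the post-resumption period with its 30 days.
- Where general event collection stops at conditioning (Section 2, Table 3 footnote e), end time at risk there and count only events with onset before it. For the event categories still collected to 30 days, use the full 30-day window.

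If the numerator is restricted instead, first set one exposure-end rule for both arms. Simply cutting events at the Section 6.4 end dates would still count 18 to 23 post-dose days for chemotherapy and none for ASP2215.

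If comparability with the ISS or the primary CSR is needed, show the exposure-only rates alongside, labelled as such.

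The cost is one extra derived variable from dates the SAP already uses (with a separate end date for the categories still collected after conditioning) and a few sentences. Reported rates will fall, noticeably so where exposure is short.

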3.2 Study Design

3.2.1 Study Design

This is a phase 3, open-label, multicenter, randomized study to compare the efficacy and safety of ASP2215 therapy to salvage chemotherapy in FLT3-mutated AML subjects who are refractory to or have relapsed after first-line AML therapy. Approximately 140 centers in North America, Europe, Asia and rest of the world will participate in this study.

Three hundred sixty nine subjects will be randomized. The randomization of the 369 subjects will be in a 2:1 ratio to receive ASP2215 or salvage chemotherapy. Subjects will enter the screening period up to 14 days prior to the start of treatment. Prior to randomization, the Investigator will preselect a salvage chemotherapy regimen for each subject; options will include LoDAC, azacitidine, MEC or FLAG-IDA. The randomization will be stratified by response to first-line therapy and preselected salvage chemotherapy. Subjects will be administered treatment over continuous 28-day cycles and per institutional guidelines for chemotherapy product preparation and administration. The dose and duration of study treatments are outlined in Section 5.1.1 of the protocol.

For subjects taking ASP2215, LoDAC or azacitidine, treatment should continue until the subject meets a treatment discontinuation criterion.

Subjects receiving MEC or FLAG-IDA will receive 1 cycle of therapy and will be assessed for response on or after day 15, per institutional guidelines. If the bone marrow cellularity is

20% or greater with at least a 50% reduction in blasts, the subject may receive a second cycle of the same chemotherapy. If bone marrow cellularity is between 5% and 20%, the investigator should make the decision whether the subject should receive another treatment cycle or be observed for recovery. If bone marrow cellularity is 5% or less, the subject will be observed for recovery. Subjects achieving CR, CRi or CRp may receive a second cycle of chemotherapy at the Investigator's discretion. Subjects with no response (NR) or progressive disease following cycle 1 will discontinue study treatment.

Dose adjustments for ASP2215 are described in Section 5.1.2 of the protocol.

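### AESI tables give only percentages of subjects over TEAE windows of unequal length, so ASP2215 can show the higher percentage at equal hazard

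*SAP*

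**What the plan says.** **Window.** SAP 6.2 fixes the end of the TEAE period: "All adverse events collected that begin within 30 days after taking the last dose of study drug will also be counted as TEAE". Section 7.5.1 uses the same span: "All adverse event (AE) recorded on treatment including within 30 days from the last study treatment will be summarized".

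**Regimens.** Section 3.2.1: "Subjects will be administered treatment over continuous 28-day cycles". The chemotherapy schedule (Section 2, Table 2, footnote n) refers to "subjects receiving MEC (days 1 through 5) or FLAG-IDA (days 1 through 6"), and adds that "MEC and FLAG-IDA are administered for up to 2 cycles depending on response and safety assessments". The other regimens are open-ended: "For subjects taking ASP2215, LoDAC or azacitidine, treatment should continue until the subject meets a treatment discontinuation criterion".

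**Measures.** In 7.5.1 the overview table and the main SOC/PT tables give percentages of subjects and also event counts adjusted by patient-year of drug exposure. Both lists include TEAEs leading to death, all and drug-related. For AESIs (all, Grade 3 or higher, drug-related Grade 3 or higher) the only measure is: "The number and percentage of subjects with TEAE of special safety interest (AESI), as classified by AESI category and PT will be summarized". A later paragraph of 7.5.1 adds: "AE summary tables will include subject counts as opposed to AE counts".

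**Related rules.** Section 6.4 ends ASP2215 exposure at the last dose and credits chemotherapy with 28 days per cycle, cut at death. Appendix 3 limits differentiation syndrome to the first 90 days. Section 7.5 presents safety by treatment group.

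**The concern.** A percentage of subjects with an event is a cumulative risk over the period in which events are counted. Here the regimen sets that period. A MEC or FLAG-IDA subject is counted for five or nine weeks, an ASP2215 subject for as long as treatment lasts plus 30 days. Side by side, the two columns mix the risk of the drug with the time each arm was watched.

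The AESI categories are the events singled out for closest scrutiny, yet they lack the exposure adjustment that the SAP already applies to its other main AE tables. The end-of-study analysis is restricted to safety, so these tables are among its main products. What is at stake is interpretation: an AESI excess on ASP2215 could be partly or wholly a matter of window length, and nothing in the AESI tables would show it. Late control events cannot be added afterwards either, because long-term follow-up collects only SAEs related to ASP2215 (Section 2, Table 3, footnote g).

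**Working it through.** **1. The plan's own figure.** The AE section states none. The survival assumptions in Section 4 supply death hazards for the illustration, so I checked those: events = (z for 0.0245 + z for 0.90)² / [(2/3)(1/3)(ln 0.65)²] = 257, and 258 deaths give 90.2% power. The stated 258 deaths and about 90% are reproduced.

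**2. Windows (last dosing day + 30).**
- MEC: 5 + 30 = day 35; with a second cycle, 28 + 5 + 30 = day 63.
- FLAG-IDA: 6 + 30 = day 36, or 28 + 6 + 30 = day 64.
- ASP2215: last dose + 30, with no fixed end.

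**3. AESI percentage at equal hazard.** From Section 4, medians of 7.7 and 5 months (30.4375 days per month) give death hazards d of 0.002957 and 0.004555 per day. Assumptions that are not in the SAP: AESI risk 5% by day 35, so a = −ln(0.95)/35 = 0.001466 per day in both arms; ASP2215 stopped for reasons other than death after a mean m of 60, 120 or 180 days (exponential, μ = 1/m).

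For a fixed window w: P = a/(a+d) × [1 − exp(−(a+d)w)].
For stopping time + 30: P = a/(a+d) × [1 − exp(−30(a+d)) × μ/(μ+a+d)].

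- One-cycle MEC: 0.2434 × (1 − 0.8100) = 4.6%. Two cycles: 7.7%. Half with two cycles: 6.2%.
- ASP2215, m = 60: 0.3313 × (1 − 0.8757 × 0.7903) = 10.2%.

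The planned table pools the controls. For this I assume half are on LoDAC/azacitidine with the same stopping pattern as ASP2215, and half of the high-intensity controls get two cycles. At m = 60 the low-intensity half shows 9.4%, so the pool is (6.2 + 9.4)/2 = 7.8%. The early-loaded case lets the hazard halve every 56 days, still 5% by day 35, integrated numerically.

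| Mean time to stop | ASP2215, constant | Pooled control, constant | ASP2215, early-loaded | Pooled control, early-loaded |
|---|---|---|---|---|
| 60 d | 10.2% | 7.8% | 7.6% | 6.4% |
| 120 d | 14.2% | 9.3% | 8.7% | 6.9% |
| 180 d | 17.0% | 10.4% | 9.3% | 7.2% |

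Part of each gap comes from the higher control mortality, which shortens observation further.

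**4. Differentiation syndrome.** The 90-day cap limits the imbalance without removing it. With death ignored and observation complete to day 90, 1 − 0.95^(90/35) = 12.4%, against 5% by day 35.

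**5. Fatal TEAEs.** As crude percentages at the design hazards, one-cycle MEC gives 1 − exp(−0.004555 × 35) = 14.7% and two cycles 24.9%. ASP2215 gives 1 − exp(−30d) × μ/(μ+d) = 22%, 32% and 40% for m = 60, 120 and 180, although its hazard is 35% lower.

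The planned rate divides by exposure as defined in Section 6.4:
- ASP2215: mean exposure 1/(μ+d) = 51.0, 88.6 and 117.5 days, so 1.60, 1.34 and 1.25 per patient-year.
- One-cycle MEC: mean exposure [1 − exp(−28d)]/d = 26.3 days, so 2.05 per patient-year.

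The direction is right, but the ratio shown is 0.78, 0.65 and 0.61 against a design value of 0.65. The numerator includes the 30-day tail and the ASP2215 denominator does not. For a subject followed throughout, window/exposure is 35/28 = 1.25 for one-cycle MEC, but 58/28 = 2.07, 114/84 = 1.36 and 198/168 = 1.18 for ASP2215 at 28, 84 and 168 days of exposure.

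**6. Check of the proposed measures.** First events per patient-year, with time at risk to first event, death or window end, give a × 365.25 = 0.535 in every group when the hazard is constant. When it is early-loaded, the rate leans the other way: 0.27-0.39 on ASP2215 against 0.35-0.44 in the pooled controls. AESI incidence through day 35 is about 4.7-4.8% on ASP2215 and 4.6-4.7% on one-cycle MEC under both shapes. That is why the rate should not stand alone.

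**The case against.** **Fatal events are already covered.** A reader might infer that fatal TEAEs, like AESIs, are compared by percentages alone. They are not. Section 7.5.1 plans patient-year rates for TEAEs leading to death in the overview and by SOC/PT, and at the design hazards those rates point the right way. Mortality itself is compared by the stratified log-rank test on OS. This objection stands, and only the two narrow remarks in step 5 remain.

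**No table sets ASP2215 against MEC/FLAG-IDA.** A reader might also infer that the AESI table will show 10-17% against about 5%. That control figure belongs to one-cycle MEC/FLAG-IDA, which is not a planned column. The pooled arm includes open-ended LoDAC and azacitidine, whose share the SAP does not give. This stands too: the gap shrinks, and by an unknown amount. It persists under the sharing assumed in step 3.

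**The component terms are adjusted.** AESI categories are built largely from preferred terms that carry patient-year rates in the SOC/PT tables. That helps in part. A category counts a subject once across several terms, and some categories add a grade filter or the 90-day limit, so category risk cannot be rebuilt from event rates by term.

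**It is only descriptive.** No test, difference or interval is planned for AEs, so no error rate or decision rule is affected. Agreed; the effect is on interpretation.

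**Conclusion.** The point holds for the AESI categories. They have percentages only, the windows differ by regimen, and at equal hazard the longer window can by itself produce the higher ASP2215 figure.

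The size cannot be fixed from the SAP. It depends on ASP2215 duration, the high-intensity share of controls and how early events occur. HSCT conditioning can also end much of the AE collection sooner. Under the stated assumptions, the pooled comparison is shifted by 1.2 to 2.1 percentage points if events are early-loaded (7.6 − 6.4; 9.3 − 7.2) and by 2.4 to 6.6 if the hazard is constant (10.2 − 7.8; 17.0 − 10.4). Events confined to the first five weeks would leave almost no distortion.

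For fatal TEAEs the conclusion is narrower. The crude percentage should not be read as a between-arm comparison, and the planned rate needs numerator and denominator over the same period. The documents do not support a claim that the plan leaves fatal TEAEs without exposure adjustment. Separately, the sentence on subject counts in 7.5.1 conflicts with the event-based tables in the same section.

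**What to change.** In 7.5.1:

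1. For each AESI table, add subjects with a first event per patient-year at risk. Time at risk runs from first dose to first event, death or the end of the TEAE window, with any HSCT gap handled as in 6.2. Use the same at-risk period for the fatal-TEAE rates.
2. Add either AESI incidence over a common early window (for example onset through day 35) or cumulative incidence with death as a competing event. Show it by treatment group and also by preselected chemotherapy intensity, which is a stratification factor and so is defined in both arms.
3. Keep the whole-treatment percentages, labelled as descriptive within arm.
4. Reconcile the statement that AE tables use subject counts with the planned event counts and patient-year rates.

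The cost is SAP wording and a few more tables or figures from dates already collected. The early window says nothing about late ASP2215 events, so the whole-treatment table is still needed for those. No display can supply a comparison with one-cycle MEC/FLAG-IDA beyond about day 35. Censoring at the end of the window is tied to stopping treatment, so later parts of the curves need cautious reading.
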